5.4 Dose Adjustment

Sodium nitrite dose will be modified according to this scheme:

- a) If a subject's ulcer surface decreases by more than 50% of the original area, as measured after 10 applications, a 50% reduction in the dose of sodium nitrite willtake effect for the remaining applications.
- b) If a subject's ulcer(s) increase by 50% of the original area, as measured after10 applications, a 50% increase in the dose of sodium nitrite will take effect for the remaining applications.

Dose-limiting toxicities are defined as:

- Severe stinging pain or burning sensation, requiring a 50% increase in opioiduse.
- •Peripheral edema causing significant discomfort by patient subjective report.
- Clinically significant hypotension or symptomatic dizziness, tachycardia, or hypoxia as per the judgment of the PI
- •Methemoglobinemia >7%

In the event that a subject experiences dose limiting toxicity, he/she will discontinue participation in the protocol.

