5.1 Study Design and Methods

5.2 Overview

This will be randomized, placebo controlled, double blinded study

We plan to enroll fifty subjects with homozygous sickle cell disease (HbSS), sickle-thalassemia (Hb S-ß thalassemia), HbSC, HbSD, or HbSO^{Arab}, in order to have 40 subjects complete at least 8 weeks of treatment, after an expected 20% dropout.

Subjects will receive 2% topical sodium nitrite cream twice a week for 10 weeks or placebo with vehicle only.

Subjects will have 0.1 cm of 2% sodium nitrite cream or placebo cream applied per 1 cm² of the total ulcerated area. If a subject has more than one ulcer, all of them will be treated with either "study cream" or placebo. Areas will be rounded to the nearest 1 cm². If a subject has more than one ulcer and the total sum of all of them is above 100 cm², then one of the ulcers can be enrolled

PI: [name]

^{*} If a patient does not qualify because he/she has an infection at the time of enrollment or at run-in, he/she can initiate the protocol two weeks after the infection has been cleared.

in the study, as long as it does not exceed the 100 cm² size. The other wounds will continue standard of care only. The total amount of sodium nitrite administered to each subject will vary depending upon the size of the ulcer but the treated total surface area will not exceed 100 cm² (i.e., subjects will receive a maximum of 10 cm of sodium nitrite cream).

Administration of study cream or placebo will be double blinded. The pharmacist will not be blinded, so he/she will be aware of who is receiving the investigational drug for safety purposes.

Randomization:

Randomization will be stratified by use of hydroxyurea to minimize its potential confounding effect on the study outcomes; we expect that 50% of participants use hydroxyurea. In addition, within each stratum (use or non-use), random treatment assignment will be balanced, i.e., 1:1 allocation, within blocks. This type of stratified block-randomized allocations will be generated by the study statistician applying a computer algorithm. The randomized allocation will occur once a subject is determined to be eligible for participation after the screening visit and the run in phase, but prior to the first cream application.

Un-blinding Procedures:

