Rationale for the study of changes in microbiome. One of the most studied effects of NO is its bactericidal and general antimicrobial activity. NO exhibits nitrosative and oxidative action alone and after reacting with oxygen, such as peroxy-nitrite, RSNOs, and nitrogen dioxide⁴¹. These species affect microbial proteins, DNA, and metabolic enzymes, disrupting cellular walls and functions. NO acts on both planktonic bacteria and biofilm communities⁴². It is likely that a significant portion of the wound healing properties of NO are mediated through its bactericidal properties, through a reduction in biofilm and inflammation. We propose to examine changes in the microbiome.

Rationale for the sodium nitrite dose: The completed phase I, dose-escalating study identified the 2% concentration as the most effective for wound healing. Two of the three subjects in this cohort experienced complete closure, for a healing rate of 86%, higher than any of the other cream concentrations. The maximum sodium nitrite dose that will be administered to patients at this dose level is 55 mg per dose. This amount of sodium nitrite is 18% of the total sodium nitrite dose that is approved by the FDA for use in the emergency treatment of cyanide poisoning (i.e. 300 mg), and is predicted to produce a peak whole blood sodium nitrite concentration of approximately 29 µmol/L if given as an intravenous bolus or 5 µmol/L if infused over 15 minutes. These levels of systemic nitrite should be safe, as similar nitrite concentrations were observed and well tolerated in one of our healthy volunteer studies (05-H-0088). A median (range) nitrite peak concentration of 20 µmol/L and a steady state level of 8 (4 – 12) µmol/L were attained during the phase I study, significantly lower than what was previously reported to be safe. This indicates that sodium nitrite is minimally absorbed when applied topically, even on abraded skin. Methemoglobin reached 4.1% at its highest level in one subject, while did not change from baseline in any of the other 17 subjects. Mean arterial blood pressure did not change, while diastolic blood pressure decreased below a predetermined threshold of 50 mmHg in 2/3 subjects at this dose level. There was no correlation between nitrite and nitrate levels and changes in BP.

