Week 2-10/ Visits 4-22: The subjects will be seen twice a week for cream application, wound care and monitoring of side effects. The wound will be measured once a week manually by the wound care nurse and measured by photography after 10±2 applications. Blood pressure and vital signs will be measured upon arrival to outpatient unit and 30 minutes±10 minutes after the application of the study cream, unless clinically indicated. If the blood pressure is stable after cream application for all visit 4, 5, 6, post cream application blood pressure monitoring wound not be needed for future study visits. The wound will be cleaned and study cream will be applied.

Routine bloods will be drawn as clinically indicated. A research methemoglobin level will be obtained every other week.

A repeat pregnancy test will be performed at week 4 in women of reproductive age. Pain assessment: a VAS scale will be obtained with each application of the study cream. If there is more than one ulcer, individual VAS scale per ulcer will be obtained.

After the first three subjects have completed the first application of the study drug, if there are no significant side effects, especially significant changes in BP, patients will be offered the option of applying the second weekly dose of the cream at home, by themselves or by a home health nurse. We will dispense the exact amount of cream to be applied eachweek. This will reduce the number of visits to the wound care / hospital location to once a week.

End of study: Subjects will return the week after the last application to have the study cream removed and for end of study procedures. Blood pressure and vital signs will be measured with a pulse oximeter. The surface area of all ulcerated surfaces will be measured and photographed with defined lighting, distance, exposure, and camera. The wound doctor or nurse will remove the "study cream" and obtain a repeat microbiome sample. A VAS scale will be obtained to assess pain. If there is more than one ulcer, individual VAS scales will be obtained per ulcer. ASCQ-ME, PROMIS, BDI, and BPI surveys will be distributed to the patient. Study labs will be obtained (see Appendix 1). Patients who discontinue the study will still receive end of study procedures.

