7.2 Stopping Rules

The study medication will be stopped if the subject experiences healing of the ulcer.

Subjects will be removed from therapy should one or more of the following occur:

- If any methemoglobin reading is >7.5%, the research study cream will be discontinued.
- Investigator or patient considers discontinuation of the study to be in the patient's best interest.
- Clinically significant hypotension (decrease in the systolic BP >20mmHg from the baseline systolic BP and of 10mmHg from the baseline diastolic BP application, and symptomatic dizziness, tachycardia, or hypoxia as per the judgment of the PI).
 - A dose will be skipped if the subject has a systolic blood pressure of ≤80mmHg and/or a diastolic blood pressure of ≤50mmHg, once the blood pressure has been checked with a repeat blood pressure check. If three doses are skipped in a row for this reason, the subject will be removed from therapy.
- Sustained pulse oxygen saturation below 85% for >15 minutes while on supplemental oxygen (up to 4L by NC).

- Increased ulcer pain requiring increased opioid use by 50%.
- Development of osteomyelitis or other systemic infection while on therapy.
- Lack of compliance, as measured by missing more than two sequential cream applications and/or at the PI's discretion.

Rules for Stopping the Study:

- Occurrence of severe toxicities:
 - Three subjects requiring sodium nitrite cream discontinuation
 - Death while on protocol, if it is attributable to the sodium nitrite cream

8. **Analysis of the Study**

We will first review and summarize data using descriptive summaries and graphical analyses to ensure recorded values are within appropriate ranges, in order to check for outliers and abnormal values. We will explore the success of randomization by comparing groups on potential confounding variables, and will include variables that are not equally distributed between groups in multivariable models. For primary analyses, we will adhere to the intent-totreat analysis principle that assigns groups as randomized as opposed to actually treated. For sensitivity analyses, we will conduct as-treated analysis and use incomplete data as well after imputation of missing data due to early dropouts; imputation methods such as last-observationcarried-forward or MCMC will be conducted and results from thereof will be compared.

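### The mid-point dose increase in section 5.4(b) has no ceiling and conflicts with the stated maximum of 10 cm (55 mg) per application for starting areas of 67 cm² or more

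*Combined protocol and SAP*

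**What the plan says.** Section 5.2 (Overview) sets the dose at 0.1 cm of cream per cm² of ulcer, with areas rounded to the nearest 1 cm². It states that "the treated total surface area will not exceed 100 cm²" and gives the consequence that "subjects will receive a maximum of 10 cm of sodium nitrite cream".

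The paragraph on the rationale for the dose, in the same section, turns this into milligrams: "The maximum sodium nitrite dose that will be administered to patients at this dose level is 55 mg per dose". It compares that amount with the 300 mg approved for cyanide poisoning (18%). It also predicts peak whole-blood concentrations of about 29 µmol/L for an intravenous bolus and 5 µmol/L for a 15-minute infusion.

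Section 5.4 has two mid-point rules, applied after 10 applications. Rule (a) halves the dose if the ulcer has shrunk by more than half. Rule (b), for ulcers that have grown by 50% of the original area, says that "a 50% increase in the dose of sodium nitrite will take effect for the remaining applications". Rule (b) names no upper limit and does not refer to section 5.2. The schedule of assessments places dose modification at visit 13, with a window of visits 11 to 15, and adds nothing about a limit.

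**The concern.** A maximum dose and a rule for raising the dose should fit together. Here they do not for subjects with large ulcers. A site with such a subject either gives more than the maximum in section 5.2 or gives less than the increase ordered in 5.4(b), and no sentence says which instruction governs.

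The maximum matters because the dose rationale argues safety from 55 mg: the 18% comparison and both predicted concentrations are figures for that amount. Section 8.1 makes tolerability and adverse effects the primary endpoint. If 5.4(b) is applied as written, the largest dose the plan permits is 1.5 times the one its safety argument describes.

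**Working it through.** **Inputs.** 0.1 cm of cream per cm², whole-cm² rounding and the 100 cm² limit (section 5.2); 5.50 mg of sodium nitrite per cm of cream (section 10); 300 mg reference dose (section 5.2, dose rationale); multiplier 1.5 (section 5.4(b)).

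**The plan's own maximum.** 100 × 0.1 = 10 cm; 10 × 5.50 = 55 mg; 55 / 300 = 18.3%. The stated 10 cm, 55 mg and 18% all reproduce.

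**Where the rules meet.** The increased dose equals the maximum when 1.5 × dose = 10 cm, so dose = 10 / 1.5 = 6.67 cm, or 66.7 cm² at 0.1 cm per cm². With whole-cm² rounding, 66 cm² stays within the maximum and 67 cm² exceeds it.

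**Size.** The dose before the increase is taken as set on the starting area. The last column is the increase still possible if 10 cm is a cap, that is 10 / dose − 1.

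| Starting area | Dose before | Dose × 1.5 | Sodium nitrite | Share of 300 mg | Increase possible under a 10 cm cap |
|---|---|---|---|---|---|
| 66 cm² | 6.6 cm | 9.9 cm | 54.5 mg | 18.2% | 50% (full) |
| 67 cm² | 6.7 cm | 10.05 cm | 55.3 mg | 18.4% | 49% |
| 80 cm² | 8.0 cm | 12 cm | 66 mg | 22% | 25% |
| 100 cm² | 10 cm | 15 cm | 82.5 mg | 27.5% | 0% |

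**Duration.** Visits 3 to 22 give 20 applications. From visit 13, 10 remain; across the window of visits 11 to 15, between 12 and 8 remain.

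**Predicted concentrations.** If these scale in proportion to dose (an assumption), 82.5 mg gives 29 × 1.5 = 43.5 µmol/L and 5 × 1.5 = 7.5 µmol/L.

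**The case against.** The best reply is that a ceiling already exists. Section 5.2 states the maximum twice in general terms, and a general maximum need not be repeated in every dosing rule. The area limit points the same way: a starting area above 66.7 cm² that has grown by half is above 100 cm² (67 × 1.5 = 100.5). Every over-maximum case is therefore also one where the treated-area limit applies. Giving 15 cm would mean treating more than 100 cm² or exceeding 0.1 cm per cm², and section 5.2 provides for neither.

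This makes a standing cap a plausible reading, but it does not remove the conflict. Section 5.2 presents 10 cm as a consequence of the area limit at the standard rate, whereas 5.4(b) changes the dose by its own rule. If the cap governs, 5.4(b) cannot be carried out as written: a subject already at 10 cm gets no increase where the text orders 50%. One of the two passages still needs an edit.

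The objection on reach stands. A starting area of 67 cm² is about 14 times the phase 1 pretreatment figure of 4.65 cm² (67 / 4.65 = 14.4), although phase 1 treated one ulcer per subject and this trial generally treats all of them. The subject must also be on active cream and have ulcers that grow by half, while in phase 1 all but one subject's ulcer shrank.

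A reader might infer a lower threshold by assuming that the dose follows the current area, because "The wound will be measured once a week manually by the wound care nurse" and "We will dispense the exact amount of cream to be applied eachweek". The documents do not support that. No sentence orders weekly recalculation, the second quote concerns supply for home application, and the schedule has a single dose modification. Raising the dose with area and then by 50% more would count the same growth twice, and the paired rules in 5.4 would have little purpose if the dose already tracked area.

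**Conclusion.** The inconsistency is real and narrow. For a starting area of 67 cm² or more, section 5.4(b) either exceeds the stated maximum, by up to 5 cm or 27.5 mg per application, or cannot be given in full. This assumes that the dose before the increase is set on the starting area and is itself held to 10 cm. Nothing in the plan is miscalculated. Few subjects, possibly none, would meet all the conditions, and no endpoint, power figure or planned analysis changes.

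A reader might also infer that 82.5 mg applied topically is unsafe. The documents do not show that. The dose rationale concludes from phase 1 that "sodium nitrite is minimally absorbed when applied topically". Section 9.3 reports about 300 mg given intravenously to eight healthy volunteers without adverse events. The safeguards continue after any increase, among them "If any methemoglobin reading is >7.5%, the research study cream will be discontinued", the dose-limiting toxicities in 5.4 and the blood-pressure rule for skipping doses in 7.2. What is shown is that the maximum on which the safety rationale rests is not the largest dose that the literal rule permits. That is worth correcting because it is a dosing instruction and the correction is simple.

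**What to change.** Add one sentence to section 5.4(b): *The increased dose may not exceed 10 cm (55 mg) per application.* The cost is that a few subjects with large ulcers receive an increase of 0% to 49% instead of 50%.

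If a higher dose is intended, restate the maximum in section 5.2, in both the Overview text and the dose rationale, as 15 cm (82.5 mg, 27.5% of 300 mg), and update the predicted concentrations. Under dose proportionality they become 43.5 and 7.5 µmol/L. The cost is a less favourable stated maximum in the safety rationale.

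Neither option needs extra patients or procedures.

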The medical monitor may request unblinding to attribute toxicities if a serious adverse event occurs to determine attribution, or if a dose limiting toxicity occurs to determine if placebo or active treatment was used.

A run in period of at least 2 weeks will be conducted, during which patients will receive/optimize wound care at the Center that will enroll the subjects, following standard of care, routinely available therapies. Patients that experience a reduction of their wound size by >25% during this time will be excluded from the trial, as this suggests an effect secondary to improved wound care only. These patients will remain on protocol and their wound will be measured monthly for up to 6 months or until closure, whichever comes first. If a subject develops an acute vaso-occlusive episode and is hospitalized during the run in period, he/she will have the run in period extended in order to allow the subject to be safely discharged from the hospital and return to outpatient care.

Close monitoring of VSS, especially BP, will be done, to assess changes in patients receiving study cream, compared to placebo.

Measurements of all leg ulcers and photographs will be obtained at the following points: At Baseline

After the 2 weeks run in period, to determine eligibility for study cream application
At mid-point: after 10 applications of study cream, to determine the need for drug modification
At end of study: after the last application of the study cream

An accurate assessment of pain will be obtained each time that size measurements are obtained.

Quality of life questionnaire (ASCQ-Me) will be given before initial application and at the end of protocol or when the ulcer(s) is (are) healed, whatever comes first.

We will monitor metHb level as a safety measure, despite the fact that the phase 1 study did not show significant elevations of metHb. **Teratogenicity** is not a consideration, since the phase 1 study demonstrated minimal systemic absorption of nitrite and nitrate, therefore the risk for the gonads and potential offspring is limited to nonexistent.

Among the entry studies to be obtained, a **3-4 mm skin optional biopsy** may be performed at the edge of the ulcerated area. If the patient has multiple ulcers, the surgeon/wound care expert will decide which one is the safest to biopsy. This will be done

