PI: [name] Version 5 in order to assess cutaneous vascularization (i.e., angiogenesis), inflammation (tissue II-6, TGF- \Box , etc.), and markers of neurogenic inflammation³⁶.

At the end of 10 weeks of treatment, subjects that still have an open ulcer will be offered continuation of care at Montefiore or University of Pittsburg or referred back to the community.

Subjects will be followed off treatment but on study with monthly visits for an additional six months to evaluate the long term effect of topical sodium nitrite on the host and the ulcer (how many ulcers re-open or close). These visits will consist of measurement of all wounds by light photography and a detailed history of intervening ulcer treatments. If patients cannot return to the hospital or have moved away, we will call them and obtain the information on the phone and ask for a photograph. The photo can be obtained by the patient him or herself. Thereafter, they will be followed up with phone calls once a year for a total of 2 years, to establish whether this therapy is changing the natural history of ulcers in this population.

Rationale for the selection of subjects' number and endpoints

Sample size: We plan to randomize a total of 50 subjects to sample size of 20 completers per arm (40 subjects total) after an anticipated 20% dropout rate is taken into account. This sample size is determined based on feasibility of recruitment within the budget constraint and time frame of the study; we anticipate enrolling 1~2 eligible subjects per month. Although the focus of analysis will be more on estimation of treatment effect sizes and their 95% confidence intervals, the anticipated sample size is adequate to detect 88% vs. 48% response rate, as defined by >25% reduction of ulcer size from baseline, between treatment and control groups, with >80% at a two-sided significance level of 0.05 (see table 1). We note that in the Phase 1 study we observed an 88% response rate. Therefore, our study will be adequately powered if response rate in the placebo group is smaller than 48%.

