8.1 Primary Endpoints and Analysis

The primary endpoint of this phase II study will be the assessment of tolerability and occurrence of adverse effects of topical sodium nitrite compared to placebo.

- 8.1.1 Frequency of each adverse event will also be tabulated. To compare the safety of prolonged (10 weeks) treatments between the experimental/treatment and usual care/placebo groups, we will apply a non-parametric Mann-Whitney test on the number of adverse events.
- 8.1.2 Effect sizes of the treatment on the ulcer size reduction will be determined by differences in response rates or odds-ratios, and the 95% Cl's will accordingly be To test if topical sodium nitrite accelerates wound healing, as defined by >25% improvement over placebo arm, we will apply a Chi-square test. Logistic regression models will be applied if inclusion of confounding variables deems necessary. We will also test if declines of weeklymeasured absolute ulcer size on a continuous scale over the study period will be different between the two groups by applying mixed effects linear models for analysis of repeatedmeasure outcomes.
- 8.1.3 Effect sizes of the treatment on the pain reduction will be determined by differences in response rates or odds-ratios, and the 95% CI's will accordingly be estimated. To test if topical sodium nitrite decreases pain at the wound site >20% over placebo, we will apply a Chisquare test. Logistic regression models will be applied if inclusion of confounding variables deems necessary. We will also test if declines of weekly-measured absolute pain VAS scores on a continuous scale over the study period will be different between the two groups by applying mixed effects linear models for analysis of repeated-measure outcomes.

25

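### Section 5.4 ends protocol participation after a dose-limiting toxicity where 7.2 only stops the cream. Read literally, 5.4 makes later ulcer, pain and follow-up data missing because of toxicity, and the two sections conflict on two triggers.

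*Combined protocol and SAP*

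**What the plan says.** Section 5.4 (Dose Adjustment) lists four dose-limiting toxicities and gives one consequence: "In the event that a subject experiences dose limiting toxicity, he/she will discontinue participation in the protocol".

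Section 7.2 (Stopping Rules) covers overlapping events with a different consequence: "Subjects will be removed from therapy should one or more of the following occur". It does not say whether measurements continue.

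Elsewhere the protocol separates stopping cream from leaving the study. Section 5.2 says of the period after treatment: "Subjects will be followed off treatment but on study with monthly visits for an additional six months", and then "Thereafter, they will be followed up with phone calls once a year for a total of 2 years". Subjects excluded at run-in for early healing are also retained: "These patients will remain on protocol and their wound will be measured monthly for up to 6 months".

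For discontinuers, the end-of-study paragraph in Section 5.3 says: "Patients who discontinue the study will still receive end of study procedures". The only timing in that paragraph is: "Subjects will return the week after the last application to have the study cream removed and for end of study procedures".

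Section 8 analyses subjects as randomized. Sections 8.1.2 and 8.1.3 add mixed models of weekly measurements, for ulcers of "absolute ulcer size on a continuous scale over the study period", with a matching model for pain scores. Imputation for early dropout appears only as a sensitivity analysis.

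**The concern.** A literal exit from the protocol turns a safety event into missing efficacy and follow-up data. The loss follows from an event after randomization that may be more common with active cream, so it need not be balanced. A mixed model uses whatever values are available and in effect projects the missing course from subjects who stayed on cream. That is a doubtful stand-in for subjects who stopped because of toxicity.

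The long-term aim suffers as well. Under 5.4 as written, a subject excluded at run-in who never received cream is measured monthly for up to six months, while a subject harmed during treatment is not.

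The second issue is operational. If 5.4 and 7.2 define the same event differently, two sites can handle the same patient differently, and it is unclear which events count toward the study-level stop after three sodium nitrite discontinuations.

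**Working it through.** **The plan's own figures.** Section 5.2 randomizes 50 to leave 40 completers after 20% dropout: 40 / 0.8 = 50, or 25 per arm at 1:1. Its power statement (over 80% for 88% against 48%, 20 per arm, two-sided 0.05) also reproduces: 0.821 by exact enumeration with the uncorrected chi-square test, 0.797 by the pooled normal approximation. This point challenges neither figure.

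**Weekly ulcer values at risk.** Section 5.3 measures the wound weekly in weeks 2 to 10 and again at end of study, taken here as week 11. The week 1 measurement precedes the first cream. A completer therefore gives 9 + 1 = 10 values after the first application, and the active arm gives 25 × 10 = 250.

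Suppose the last application is in week w and the end-of-study visit is the following week:

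- kept = (w − 1) weekly values + 1 end-of-study value = w
- lost = 10 − w
- end-of-study visit in week w + 1, which is 10 − w weeks early

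With k active-arm exits, the share lost is k(10 − w)/250.

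| Last application | End-of-study visit | Weeks early | Values lost per subject | k = 1 | k = 2 |
|---|---|---|---|---|---|
| Week 1 | Week 2 | 9 | 9 | 3.6% | 7.2% |
| Week 5 | Week 6 | 5 | 5 | 2.0% | 4.0% |
| Week 9 | Week 10 | 1 | 1 | 0.4% | 0.8% |

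Pain values are lost too, because Section 5.3 ties the pain score to each cream application. They are not counted here.

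**Monthly visits.** 25 × 6 = 150 in the active arm. One exit loses 6 (4%) and two lose 12 (8%).

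**Responder status.** It is not missing, because the exit assessment supplies a value. If that value is early and the subject's status would have differed at the planned visit, each such subject moves the active-arm rate by 1/25 = 4.0 points, and two move it by at most 8.0.

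**Can an early value differ from a planned one?** In phase 1 Table 1 (Section 2.4), mean percent healed between week 3 and end of study went from 55.1 to 88.6 at 2.0%, from 22.5 to 32.9 at 1.5%, and from 15.8 to 3.8 at 1.0%. These are small on-treatment cohorts. They show only that ulcer size can change quickly, not what happens after cream stops. At this trial's 2.0% dose the week 3 mean was already well above the 25% response threshold.

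**Triggers side by side.**

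| Event | Section 5.4 | Section 7.2 |
|---|---|---|
| Methemoglobin | above 7% | above 7.5% |
| Hypotension | clinically significant hypotension or symptoms; no mmHg figure | systolic fall above 20 mmHg and diastolic fall of 10 mmHg, and symptoms |

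A reading of 7.1% to 7.5% ends participation under 5.4 and does not meet the 7.2 threshold. Symptomatic dizziness without the pressure falls meets 5.4 and not the 7.2 hypotension rule. Any event that meets either of these 7.2 rules also meets 5.4, so 5.4 is the stricter in both cases.

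**The case against.** The strongest reply is that 5.4 is loose wording for the end of treatment. Section 7.2 speaks of therapy only, the monthly follow-up in 5.2 makes no exception for discontinuers, and 5.3 gives them end-of-study procedures. This reading is available, so the loss cannot be stated as certain. It still requires a site to set aside what 5.4 says. Section 12.2, which has the investigator follow an event until it resolves, also fits poorly with ending participation.

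The early timing of the exit visit is likewise an inference. The schedule of assessments places end of study after week 10 with a window of ±3 days, and no text sets the timing for discontinuers. It is an ambiguity, and the weeks-early figures hold only on one reading.

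The impact is also modest. The declared primary endpoint is tolerability and adverse events. Section 12 collects these only during treatment, so that comparison barely changes. The plan allows for 20% dropout and compares imputation methods as sensitivity analyses. Section 8 names no six-month test. These points limit the size. A dropout allowance protects the number of completers, but it does not address data missing because of toxicity.

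A reader might infer two stronger points that the documents do not support. One is a large power loss from counting exits as non-responders: no text says they are so counted, and an exit measurement exists. The other is that Table 2 in Section 12 adds a third set of discontinuation triggers: it lists expected adverse events and is not a stopping rule.

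**Conclusion.** The inconsistency is real and should be corrected, though its numerical effect is likely to be small. Read literally, 5.4 makes later weekly ulcer and pain values, monthly visits and yearly calls missing because of toxicity, in an analysis that groups subjects as randomized. The direction of any bias is unknown.

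The percentages are illustrative. No toxicity rate at this dose and duration is given, and one or two active exits is an assumption suggested by the study stop at three sodium nitrite discontinuations. That cap is not firm: the stop is listed under severe toxicities, so milder 5.4 exits may not count, and placebo exits are not capped. The effect also depends on timing. A week 9 exit loses almost nothing, and Section 5.2 would count that subject as a completer.

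The methemoglobin and hypotension conflicts between 5.4 and 7.2 stand on the text alone and need no assumption.

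**What to change.** 1. In 5.4, replace the consequence with: *will discontinue study cream but remain on study*. Say the same in 7.2.
2. Unless consent is withdrawn, keep the weekly ulcer and pain measurements after cream stops where feasible. At minimum keep the planned assessment after week 10 and the six monthly visits. State that pain scores are then taken without an application.
3. In 5.3, state when discontinuers have their end-of-study procedures.
4. Use one methemoglobin and one hypotension definition in 5.4 and 7.2. Apply the stricter 5.4 triggers until the sponsor decides which values to use.
5. State which discontinuations count toward the three-subject study stop.

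The cost is a few sentences and a few off-treatment visits for affected subjects. Those visits are already scheduled for everyone else, and the sample size does not change.
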